### **12.6 Action Taken and Outcome**

Action Taken with IP or device will not be collected given the nature of this study. The Outcome of each AE will be entered as either: Recovered/Resolved, Recovered/Resolved with Sequelae, Not Recovered/Not Resolved, Fatal, or Unknown.

### **12.7 Adverse Event Follow-up**

Investigators will follow unrelated AEs until 7-days after the study visit. All SAEs, and related AEs will be followed until the event has resolved.

## 12.8 Serious Adverse Events

An AE or ADE that results in any of the following outcomes is serious:

- Death (note that death is the outcome of an SAE, and the cause of death should be listed as the AE)
- Life-threatening event. An event, in the view of either the investigator or sponsor, which places the patient or participant at immediate risk of death. (It does not include an adverse event or suspected adverse reaction that, had it occurred in a more severe form, might have caused death)
- In-patient hospitalization or prolongation of existing hospitalization
- A persistent or significant incapacity, permanent damage or disability or substantial disruption of the ability to conduct normal life functions
- Congenital anomaly or birth defect
- Other important medical event that may not result in death, be life-threatening, or require hospitalization may be considered serious when, based upon appropriate medical judgment, it may jeopardize the participant or may require medical or surgical intervention to prevent one of the outcomes listed in this definition.
- Hospitalization for elective surgery for a prior condition that did not worsen or for social reasons will not be treated as serious.

A serious adverse device effect (SADE) is a serious event that has resulted in any of the consequences characteristic of a serious adverse event. For the purpose of this study, the term SAE will include SADEs.

### 12.8.1 Serious Adverse Event Reporting

Any SAE which occurs after the Informed Consent document is signed until participant leaves site on date of visit must be reported to Lilly. Lilly must be notified within 24 hours after the site/investigator becomes aware of the SAE.

If the Principal Investigator determines that the event is serious, the following procedures will be implemented:

- The Investigator will report the SAE directly to Lilly. Contacts for SAE reporting can be found in site training materials.
- Investigator will provide, at a minimum, the protocol number, participant's initials, participant number, date of the SAE, SAE term and relationship to IP and/or device. The SAE report form should be submitted with any supporting data available or copies of CRF pages.
- Advarra IRB will be notified of the SAE by the site within the timeframes described below:

1. Unanticipated problems that are serious adverse events should be reported to the IRB within 10 business days of the investigator becoming aware of the event.
2. Any other unanticipated problem should be reported to the IRB within 10 business days of the investigator becoming aware of the problem.

An initial report followed promptly by a complete report will be forwarded to Advarra IRB.

### **12.8.2 Serious Adverse Event Follow-up**

Investigators will follow all SAEs until the SAE has resolved.

The Investigator and Medical Monitor will determine if additional follow-up is required. Follow-up information relating to an SAE must be submitted to Lilly as soon as additional data related to the event are available. All efforts must be taken to obtain follow-up information promptly.

Follow-up information may consist of:

- A hospital discharge summary for participants who are hospitalized or hospitalized over a prolonged period due to the SAE. If possible, the discharge summary should be obtained when it becomes available.
- A copy of the autopsy report, if a death occurs and an autopsy is performed, should be obtained if possible when it becomes available.

Any SAE that is ongoing at the end of visit 1 should be followed as described above. Data after visit 1 should be recorded on the source documents and submitted to Lilly on an SAE report form. For ongoing SAEs, the Principal Investigator must submit follow-up reports to Lilly regarding the participant's subsequent course until the case is closed.

### **12.9 Unexpected Adverse Event**

As defined by 21 CFR 312.32 (a), an unexpected adverse drug experience is:

“An adverse event or suspected adverse reaction is considered “unexpected” if it is not listed in the investigator brochure or is not listed at the specificity or severity that has been observed; or, if an investigator brochure is not required or available, is not consistent with the risk information described in the general investigational plan or elsewhere in the current application, as amended. For example, under this definition, hepatic necrosis would be unexpected (by virtue of greater severity) if the investigator brochure referred only to elevated hepatic enzymes or hepatitis. Similarly, cerebral thromboembolism and cerebral vasculitis would be unexpected (by virtue of greater specificity) if the investigator brochure listed only cerebral vascular accidents. “Unexpected,” as used in this definition, also refers to adverse events or suspected adverse reactions that are mentioned in the

investigator brochure as occurring with a class of drugs or as anticipated from the pharmacological properties of the drug but are not specifically mentioned as occurring with the particular drug under investigation.”

The study sponsor will expedite reporting all serious unexpected suspected adverse reactions (SUSARs): initial reporting by the sponsor for nonfatal or non-life threatening SUSARs must be submitted as soon as possible but no later than within 15 calendar days following the sponsor’s initial receipt of the information, and for fatal or life-threatening SUSARs, initial reports must be submitted no later than 7 calendar days following the sponsor’s initial receipt of the information. Any relevant additional information obtained by the sponsor that pertains to a previously submitted IND safety report must be submitted as a Follow-up IND Safety Report without delay as soon as the information is available but no later than 15 calendar days after the sponsor receives the information.

Such expedited reports will comply with the applicable regulatory requirements and with the FDA’s Guidance for Industry and Investigators Safety Reporting Requirements for INDs and BA/BE Studies (21 CFR 312.32).

### **12.9.1 Unanticipated Adverse Device Effect**

As defined by 21 CFR 812.3 (s), an unanticipated adverse device effect (UADE) is:

"any serious adverse effect on health or safety or any life-threatening problem or death caused by, or associated with, a device, if that effect, problem, or death was not previously identified in nature, severity, or degree of incidence in the investigational plan or application (including a supplementary plan or application), or any other unanticipated serious problem associated with a device that relates to the rights, safety, or welfare of participants."

The PI will report evaluation results for any unanticipated adverse device effect per 21 CFR 812.150 (b)(1) within 10 days working days to the reviewing IRB(s).

All unanticipated adverse device effects will be evaluated and reported as warranted within 10 working days after sponsor first receives notice of the effect per 21 CFR 812.46 (b) and 21 CFR 812.150 (b)(1).

### **12.9.2 Definition of Product Complaints**

A product complaint is any written, electronic, or oral communication that alleges deficiencies related to the identity, quality, durability, reliability, safety, effectiveness, or performance of a study intervention. When the ability to use the study intervention safely is impacted, the following are also product complaints:

- deficiencies in labeling information

- use errors for device or drug-device combination products due to ergonomic design elements of the product.

Product complaints related to study interventions used in clinical trials are collected to ensure the safety of participants, monitor quality, and to facilitate process and product improvements.

If the participant identifies a product complaint or a problem with the study intervention, investigators will instruct participants to contact the site as soon as possible so that the situation can be assessed.

An event may meet the definition of both a product complaint and an AE/SAE. In such cases, it should be reported as both a product complaint and as an AE/SAE.

Device deficiencies are product complaints.

### **12.9.3 Recording and Follow-Up of AE and/or SAE and Product Complaints**

When an AE/SAE/product complaint occurs, it is the responsibility of the investigator to review all documentation (for example, hospital progress notes, laboratory reports, and diagnostics reports) related to the event.

The investigator will then record all relevant AE/SAE/product complaint information in the participant's medical records, in accordance with the investigator's normal clinical practice. AE/SAE information is reported on the appropriate CRF page and product complaint information is reported on the Product Complaint Form.

Note: An event may meet the definition of both a product complaint and an AE/SAE. In such cases, it should be reported as both a product complaint and as an AE/SAE.

It is **not** acceptable for the investigator to send photocopies of the participant's medical records to the sponsor or designee in lieu of completion of the CRF page for AE/SAE and the Product Complaint Form for product complaints.

There may be instances when copies of medical records for certain cases are requested by the sponsor or designee. In this case, all participant identifiers, with the exception of the participant number, will be redacted on the copies of the medical records before submission to the sponsor or designee.

The investigator will attempt to establish a diagnosis of the event based on signs, symptoms, and/or other clinical information. Whenever possible, the diagnosis (not the individual signs/symptoms) will be documented as the AE/SAE.

## **13 INVESTIGATOR OBLIGATIONS**

### **13.1 Ethical and Regulatory Considerations**

This study will be conducted in accordance with Good Clinical Practice (GCP) Guidelines E6 (2) and the Code of Federal Regulations ( Title 21 CFR Parts 11, 50, 54, and 56).

### **13.2 Institutional Review Board**

The Concentrics Research will ensure that an appropriately constituted Institutional Review Board (IRB), in compliance with the requirements of 21 CFR 56, reviews and approves the clinical study before the study is initiated. IRB approval must refer to the study by exact protocol title, number, and amendment number (if applicable), identify the documents reviewed, and state the date of review.

Concentrics Research will ensure that Lilly approves any changes to the Informed Consent template prior to submission to the IRB.

Should changes to the Informed Consent document become necessary during the study, Concentrics Research will ensure that the changes are approved by Lilly prior to submission to the IRB. Should changes to the study protocol become necessary, the protocol amendment will be approved by the IRB prior to implementation. Protocol administrative changes will be reviewed by the IRB.

### **13.3 Informed Consent**

A properly executed, written Informed Consent, in compliance with 21 CFR Part 50 and HIPAA authorization, will be obtained from each participant prior to enrollment and the initiation of screening evaluations required by this protocol. A copy of the Informed Consent document will be reviewed and approved by Lilly for acceptability and submitted by or on behalf of the Investigator, together with the protocol, to the IRB for review and approval prior to the start of the study. The Informed Consent will be written in language fully comprehensible to the prospective participant.

### **13.4 Participant Confidentiality**

All communications, reports, and participant samples will be identified only by a coded number and/or initials to maintain participant confidentiality. All records will be kept confidential to the extent permitted by law. If a waiver or authorization separate from the statement in the Informed Consent is required for permitting access to a participant's medical records (e.g. HIPAA), the investigator will obtain such authorization prior to enrolling a participant in the study. The Principal Investigator will keep a separate log of participants,

codes, names, and addresses. Documents which identify the participant by name (for example, the Informed Consent document) will be kept in strict confidence.

Lilly and its business associates agree to keep all participant information confidential. Only coded data will be released identifying participants by participant number only. Data resulting from analyses will be entered into a database that is not accessible to the public.

Lilly and its business associates will take every possible step to reduce the risk of releasing information to the public that would enable participants to be personally identified.

## 14 APPENDICES

### 14.1 INSTRUCTIONS FOR USE

**Instructions for Use**  
**Clinical Trial J2T-MC-KGBY**  
**Study Drug (LY3650150)**  
**Prefilled Pen**  
**Injection for use in injection pad only**  
**Single-Dose Prefilled Pen**

This Instructions for Use contains information on how to inject Study Drug.

**Before you use the Study Drug Prefilled Pen (Pen), read and carefully follow all the step-by-step instructions.**

Your Pen may look different than the Pen in the pictures in this document.

[figure not shown]
**Important information you need to know before injecting Study Drug**

- You will be informed on how to prepare and inject Study Drug into the injection pad using the Pen. **Do not** inject yourself or someone else. **Do not** inject into the injection pad until you have been shown how to inject Study Drug.
- Keep this Instructions for Use and read it as needed.
- Each Study Drug Pen contains 1 dose of Study Drug. **The Pen is for one-time use only.**
- The Study Drug Pen contains glass parts. Handle it carefully. If you drop it on a hard surface, **do not** use it and contact study staff.
- The study staff will instruct you how to prepare the injection pad.
- If you have vision or hearing problems, **do not** use Study Drug Pen without help from study staff.

## INSTRUCTIONS FOR USE

Before you use the Study Drug Pen, read and carefully follow all the step-by-step instructions.

### Parts of the Study Drug Pen

## Preparing to inject Study Drug

### From the study staff, gather supplies and Study Drug Pen:

- Study Drug Pen
- 1 injection pad
- 1 alcohol wipe
- 1 sharps disposal container  
(See **Disposing of Study Drug**)

### Warm to room temperature

Study staff will have already allowed the Pen to warm to room temperature. Do not remove the gray base cap until you are ready to inject.

- **Do not** warm up the Pen with a microwave, or hot water, or direct sunlight.
- **Do not** use the Pen if the medicine is frozen.

### Inspect the Pen and the medicine

Make sure you have the right medicine. The medicine inside should be clear. It may be colorless to slightly yellow to slightly brown.

**Do not** use the Pen (see **Disposing of Study Drug**) if the:

[figure not shown]
- Pen looks damaged
- Medicine is cloudy, is discolored, or has particles

### Wash your hands with soap and water

### Prepare injection pad

Your study staff will help you prepare the injection pad for injection. To better simulate a self-injection, you will secure the injection pad to your body, on your abdomen or your thigh.

Clean the injection pad with an alcohol wipe and let dry.

You or another person may inject into these areas.

[figure not shown]
- **Stomach area (abdomen) —**  
At least 2 inches away from the belly button (navel).
- **Front of thigh —**  
At least 2 inches above the knee and 2 inches below the groin.

## Injecting Study Drug

Figures below illustrate injecting in your body. For this study, all injections are into an injection pad that is secured to your body. **Do not** inject yourself or anyone else.

**1**

### Uncap the Pen

Make sure the Pen is **locked**.

[figure not shown]
When you are ready to inject, twist off the gray base cap and throw it away in the trash.

**Do not** put the gray base cap back on; this could damage the needle.

**Do not** touch the needle inside the clear base.

**2**

### Place and unlock

[figure not shown]

**Place** and hold the clear base flat and firmly against the injection pad.

 Keep the clear base on the injection pad, then turn the lock ring to the **unlock** position.

**3**

[figure not shown]
### Press and hold for 15 seconds

**Press and hold** the purple injection button and **listen** for 2 loud clicks:

- First click: injection started
- Second click: injection completed

The injection may take up to 15 seconds.

You will know the injection is complete when the gray plunger is visible.

## Disposing of Study Drug

### Dispose of (throw away) the used Pen

Put the used Study Drug Pen in a sharps disposal container right away after use, as directed by study staff.

**Do not** throw away (dispose of) the Study Drug Pen in the trash.

## Commonly asked questions

### Q. What if I see bubbles in the Pen?

A. Air bubbles are normal. They will not harm you or affect your dose.

### Q. What if there is a drop of liquid on the tip of the needle when I remove the gray base cap?

A. A drop of liquid on the tip of the needle is normal. This will not harm you or affect your dose.

### Q. What if I unlock the Pen and press the purple injection button before twisting off the gray base cap?

A. **Do not** remove the gray base cap. Throw away (dispose of) the Pen and contact study staff to get a replacement. Use a new pen for the injection.

### Q. Do I need to hold the purple injection button down until the injection is complete?

A. You do not need to hold the purple injection button down, but it may help you keep the Pen steady and firm against the injection pad.

**Q. What if the needle did not retract after my injection?**

A. **Do not** touch the needle or replace the gray base cap. Put the Pen in a safe place to avoid an accidental needlestick and contact your study staff.

**Q. How can I tell if my injection is complete?**

A. After you press the purple injection button, you will hear 2 loud clicks. The second loud click tells you that your injection is complete. You will also see the gray plunger at the top of the clear base. The injection may take up to 15 seconds.

**Q. What if I remove the Prefilled Pen before the second loud click or before the gray plunger stops moving?**

A. You may not have given the full dose. Contact study staff.

**Q. What if I heard more than 2 clicks during my injection, 2 loud clicks and 1 soft one. Did I give a complete injection?**

A. Some people may hear a soft click right before the second loud click. That is the normal operation of the Prefilled Pen. **Do not** remove the Prefilled Pen from the injection pad until you hear the second loud click.

16. REFERENCES 18**ABBREVIATIONS**

AE	Adverse Event
AD	Atopic Dermatitis
CRF	Case Report Forms
ENR	Patients Enrolled Set
MedDRA	Medical Dictionary for Regulatory Activities
mSQAAQ	Modified Subcutaneous Administration Assessment Questionnaire
Q1	First Quartile
Q3	Third Quartile
REALM	Rapid Estimation of Adult Literacy in Medicine
SAP	Statistical Analysis Plan
SAS	Statistical Analysis Software
SD	Standard Deviation
SOC	System Organ Class

1. INTRODUCTION

This statistical analysis plan (SAP) describes the rules and conventions to be used in the presentation and analysis of the ease of use and confidence of lebrikizumab administrations via a prefilled pen. It describes the data to be summarized and analyzed, including specifics of the statistical analyses to be performed.

This statistical analysis plan (SAP) is based on protocol version 1.0, dated 12 APR 2024 and Case Report Forms (CRFs) version 1.0, dated 15 APR 2022.

2. STUDY OBJECTIVES

2.1 Primary Objective

[figure not shown]
The primary objective is to evaluate the ease of use and confidence of lebrikizumab administrations via a prefilled pen using the modified Subcutaneous Administration Assessment Questionnaire (mSQAAQ) following training on the pen.

3. STUDY DESIGN

3.1 General Description

This study is an open-label, single site ease of use study of the lebrikizumab pen and consists of a single study visit for approximately 56 adult participants. All participants will receive training and perform mock injections on a practice pad using the pen. Participants will be under the supervision of a study interviewer when handling the pen and will complete the mSQAAQ following the simulated injection.

No treatment will be administered to the participants. A Study Flowchart can be found in [Figure 1](#).

Figure 1 Study Flowchart

3.2 Schedule of Events

The schedule of events can be found in Table 2 of the protocol.

3.3 Changes to Analysis from Protocol

No changes from protocol.

Document: ELI_LILLY_JAB94256_Auto_inj_SAP_v1.0_03JUN2024

Author: PPD

Version: 2.0

Version date: 16Jul2024

4. PLANNED ANALYSES

4.1 Interim Analysis

There are no interim analyses planned for this study.

4.2 Final Analysis

The final analysis described in this SAP will be performed by IQVIA Real World (RW) Biostatistics following the database lock. The corresponding TLFs will form the basis for the clinical study report.

5. ANALYSIS SETS

5.1 All Patients Screened [SCR]

All Patients Screened (SCR) set will contain all patients screened for the study.

5.2 All Patients Enrolled Set [ENR]

All Patients Enrolled (ENR) set will contain all patients who provide informed consent for this study.

6. GENERAL CONSIDERATIONS

6.1 Sample Size

The planned final sample size of 51 participants with full data is sufficient to provide descriptive insights about the study population. Given the nature of the study it is expected that **cci**%+ of participants enrolled will complete the study and provide full analyzable data.

As defined in the protocol, under the assumption that **cci**% of the participants will respond “agreed” or “strongly agreed” to the device being “easy to use” and “they are confident they can use the device” we will have 95% confidence that the response rate is located in this range of proportions: **cci**% - **cci**%. [Table 1](#) shows a variety of possible sample sizes. For the purpose of the intended claims the 95% CI lower bound should remain above **cci**%, preferably above **cci**%, and the parameters for the calculation of sample size have been selected for that.

Table 1 Sample Size Calculation

Proportion	Margin	Lower CI	Upper CI	Sample Size
95.0%				
95.0%	CCI			
90.0%				
85.0%				
80.0%				

6.2 Baseline

This is a single center, single visit simulated use study. All participants will complete the study at the end of Visit 1. For the purpose of this study, baseline refers to Visit 1. Day 1 is also referred to as Visit 1.

6.3 Baseline Data

Baseline data is defined as data collected at Visit 1.

Document: ELI_LILLY_JAB94256_Auto_inj_SAP_v1.0_03JUN2024

Author: PPD

Version: 2.0

Version date: 16Jul2024

6.4 Windowing Conventions

This study will require one visit. Subjects will be enrolled and completed at Visit 1.

6.5 Software Version

All analyses will be conducted using Statistical Analysis Software® (SAS) version 9.3 or higher.

7. STATISTICAL CONSIDERATIONS

7.1 Statistical Tests and Confidence Intervals

Continuous variables will be summarized using descriptive statistics, i.e., by the number of non-missing and missing observations, mean, standard deviation (SD), first quartile (Q1), median, third quartile (Q3), minimum, and maximum.

Categorical variables will be summarized by frequency counts (n) and percentages (%). Percentages will not include the missing category and are calculated over the number of patients with available (non-missing) data. Counts of missing data will be provided in the tables for information only.

For reporting conventions, percentages will be reported to 1 decimal place unless greater precision is deemed appropriate, except for cases when 100% is presented. In cases of a count of 0, the percentage will not be presented. The 95% confidence interval (CI) for the response rates will be calculated using Clopper-Pearson method.

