## 2 STUDY SYNOPSIS

Name of Company: Eli Lilly & Company (Lilly)
Protocol Number: #23037 (J2T-MC-KGBY)
Name of Investigational Product/Active Ingredients: Lebrikizumab Pen
Title of Study: Study to Assess Lebrikizumab Pen Ease of Use in Patients with Atopic Dermatitis
Name of Contract Research Organization (CRO): Concentrics Research, an IQVIA Business
Participant Environment: The participant environment will be non-clinical and emulate the noise, lighting, and surroundings of a home environment. Study rooms are equipped with 1-way mirrors, cameras, and remote monitoring equipment for participant observation. There will be 1 research site used in this study.
Study Type: Ease of use with a simulated injection
Objective: To evaluate the ease of use and confidence of lebrikizumab administrations via a prefilled pen using the modified Subcutaneous Administration Assessment Questionnaire (mSQAAQ)  following training on the pen.
Design This study is an open-label, single site ease of use study of the lebrikizumab pen and consists of a single study visit for approximately 51 adult participants. All participants will receive training and perform simulated injections on an injection pad using the pen. Participants will be under the supervision of study site staff when handling the pen and will complete the mSQAAQ  following the simulated injection. No treatment will be administered to the participants.
Study Population The study population will be comprised of adults, ages 18 and older, who have been diagnosed with Atopic Dermatitis (AD). These participants will be pen and autoinjector (AI) naïve (i.e., not previously used a pen or AI); however, they will be permitted to participate if they have other injection experience (e.g., pre-filled syringe [PFS]).
Recruitment One research site will be used for this study, the Concentrics Center for Research in Indianapolis, IN. Participants will be recruited from the site's database. Approximately 56 participants will be enrolled with 51 participants planned to complete the study. Recruitment will include telephone prescreening based on the inclusion and exclusion criteria and collection of demographics. A broad range of participants will be recruited to assure racial and ethnic diversity that approximates the U.S. Census. 

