#### **6.3.5 Removal of Individual Participants from Therapy or Assessments**

The following may result in a participant being removed prematurely from study participation:

- A participant withdraws consent to participate in the study.
- A participant was erroneously included in the study.
- The study is terminated by the Sponsor.
- A participant is unable to comply with study procedures (e.g., under the influence of drugs or alcohol or participant is combative)

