## 10.3 Data Management & Statistical Analysis

### 10.3.1 Data Analysis

A descriptive analysis will be conducted to assess the ease of use and confidence of use of the lebrikizumab pen. All participants having given an informed consent will be included in the analysis population.

The main endpoint of the study will be assessed via the mSQAAQ. The primary outcome reported from each individual question will be the proportion of participants responding “agreed” or “strongly agreed” to the question. Participants who do not complete an individual item in the mSQAAQ will have their remaining questions analyzed per instrument instructions.

Collected demographic information and health literacy level of study participants will be presented for the total analysis population as well as any selected sub-populations. A descriptive analysis of any AEs and/or product complaints reported during the study will be included for the total analysis population.

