7.2 Missing data

Missing data will not be imputed. All analysis will be conducted based on the observed data. Any participants who attend a study visit but do not complete the simulated injection will be excluded from the analysis. Partial completion of the mSQAAQ will be analyzed per the instrument instructions.

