9. DISPOSITION AND WITHDRAWALS

All patients who provide informed consent will be accounted for in this study. Subject disposition will be summarized in terms of number and percentages (n, %) for the below variables (see [Section 7.1](#) for more details). Unless specified otherwise, percentages will be calculated using the number of patients from ENR as denominator.

- Patients in SCR.
- Patients in ENR.
- Patients not meeting eligibility criteria.
- Patients who completed the study.
- Patients who discontinued the study.
- Reason for study discontinuation.
 - Adverse Event or Serious Adverse Event
 - Noncompliance with Protocol
 - Withdraw consent
 - Screen Failure
 - Other

Document: ELI_LILLY_JAB94256_Auto_inj_SAP_v1.0_03JUN2024

Author: PPD

Version: 2.0

Version date: 16Jul2024

For the variables “Patients in ENR” and “Patients not meeting eligibility criteria”, percentages are calculated based on SCR as denominator.

A listing will also be provided for the above disposition data.

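### Under SAP 7.1 and 7.2, a participant who is handed the pen, does not finish and gives no answer never counts against the agreement rate for Q9 and Q11

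*SAP*

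**What the plan says.** - **Denominator.** SAP 7.1: "Percentages will not include the missing category and are calculated over the number of patients with available (non-missing) data". It continues: "Counts of missing data will be provided in the tables for information only".
- **Imputation and exclusion.** SAP 7.2: "Missing data will not be imputed. All analysis will be conducted based on the observed data". Then: "Any participants who attend a study visit but do not complete the simulated injection will be excluded from the analysis". Protocol 10.5 has a similar exclusion, but its condition names the mSQAAQ as well as the injection.
- **Population.** Protocol 10.3.1: "All participants having given an informed consent will be included in the analysis population". SAP 14.1.2 places the primary analysis on the ENR, which SAP 5.2 defines as everyone who consents, and sends each item to SAP 7.1 for its summary. SAP 3.3 declares no change from the protocol.
- **Primary items.** SAP 14.1.1 names Q9 (overall ease of use) and Q11 (confidence in using the device). Intervals are Clopper-Pearson (SAP 7.1).
- **Use of the lower limit.** Protocol 10.2 and SAP 6.1 say that the lower 95% bound should stay above a value, which is redacted, for the intended claims.
- **Planned numbers.** Protocol synopsis: "Approximately 56 participants will be enrolled with 51 participants planned to complete the study".
- **Removal and disposition.** Protocol 6.3.5 lists as a ground for removal: "A participant is unable to comply with study procedures", with intoxication and combative behaviour as its examples. SAP 9 offers as discontinuation reasons an adverse event, "Noncompliance with Protocol", withdrawal of consent, screen failure and other. None is specific to the pen task.

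**The concern.** The study asks whether people with atopic dermatitis find the pen easy to use and feel confident using it. Someone who takes the pen and stops before the end may be telling us something about exactly that. Under the plan this person leaves the result twice over. SAP 7.2 removes them because the injection was not completed. If that exclusion were lifted, SAP 7.1 would still leave them out of each percentage for which they gave no answer. No other analysis brings them back as not agreeing.

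Two things make this more than a matter of presentation. The lower confidence limit is tied to the intended claims, so a rule that moves it can matter to a decision. And naming the ENR as the primary set gives the impression that everyone who consented is represented, when the percentages do not represent them all.

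**Working it through.** **Inputs.** Planned numbers: 56 enrolled and 51 completing (protocol synopsis), so 56 − 51 = 5 without complete data, or 5/56 = 8.9%. Assumed agreement: 95% (protocol 10.2, text on Table 4). Interval: two-sided 95% Clopper-Pearson (SAP 7.1). The number k of participants who are handed a pen and leave no answer is not given; it is an assumption and is varied below.

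**The plan's own figure.** The margin behind the 51 is redacted, so 51 cannot be reproduced independently. With n = z²p(1 − p)/m² and p = 0.95, a back-solved margin of 6% gives 1.96² × 0.95 × 0.05 / 0.06² = 50.7, rounded up to 51. Margins of 5% and 7% would give 73 and 38. So 51 is consistent with a 6% margin, but that value is inferred.

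**Who is in the denominator.** Three types of participant who have been handed a pen:
1. Does not finish the injection and gives no answer: excluded by SAP 7.2, and in any case outside the SAP 7.1 denominator.
2. Does not finish the injection but answers: excluded by SAP 7.2 despite the answer. Protocol 10.5 is less clear, because its condition also names the questionnaire.
3. Finishes the injection but leaves an item blank: kept by SAP 7.2, but outside the SAP 7.1 denominator for that item only. The denominator is set per item, so it can differ between Q9 and Q11.

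The point here concerns the first type.

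**Effect on the rate.** With x agreeing among n answerers, the plan reports x/n. Counting k non-answerers as not agreeing gives x/(n + k), which is smaller for any x > 0 and k > 0. For the intervals, with N = n + k, the lower limit is the 0.025 quantile of Beta(x, N − x + 1) and the upper limit is the 0.975 quantile of Beta(x + 1, N − x). Since 0.95 × 51 = 48.45, take x = 48.

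| k | x/(n + k) | Rate | 95% CI |
|---|---|---|---|
| 0 (plan) | 48/51 | 94.1% | 83.8% to 98.8% |
| 1 | 48/52 | 92.3% | 81.5% to 97.9% |
| 2 | 48/53 | 90.6% | 79.3% to 96.9% |
| 3 | 48/54 | 88.9% | 77.4% to 95.8% |
| 5 | 48/56 | 85.7% | 73.8% to 93.6% |

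One person moves the rate by 94.1 − 92.3 = 1.8 points and the lower limit by 83.8 − 81.5 = 2.3 points. Two move the lower limit by 83.8 − 79.3 = 4.5 points. Starting from 49/51 = 96.1% (86.5% to 99.5%), one person gives 49/52 = 94.2% (84.1% to 98.8%), a similar step.

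**The opposite extreme.** If all five would have agreed, the rate would be 53/56 = 94.6% (85.1% to 98.9%), slightly above the plan's 94.1%. Leaving them out would then not have raised it.

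**The case against.** - **SAP 7.1 is not the first rule to act.** As written, SAP 7.2 has already removed a participant who did not finish the injection. Taken alone, SAP 7.1 touches only people who finished and left an item blank, and a blank is not a pen failure. This stands, and the point is therefore about the two rules together. It also shows that changing either one alone would not bring the non-finisher into the rate.
- **Pen failures are reported elsewhere.** SAP 10 tabulates observed performance of three pen tasks, certain use errors are product complaints (protocol 12.9.2), disposition is tabulated and listed, and missing counts are printed. True, and useful to a careful reader. But none of it enters the agreement rate or its lower limit.
- **Protocol 6.3.5 is not aimed at pen failures.** A reader might infer that it is a route for removing people who cannot work the pen. Its examples are behavioural. They are only examples, so the wording could stretch that far, but the documents do not say so. Nor do they say how SAP 9 would code such a person.
- **The five may never touch a pen.** Enrolment means consent. Eligibility is reconfirmed and pregnancy tested afterwards, and SAP 9 lists screen failure as a discontinuation reason. A reader might take the 8.4-point difference at k = 5 (94.1 − 85.7) as the expected overstatement; the documents do not support that.
- **The direction is not certain.** A reader might infer that missing answers can only flatter the pen. That holds against scoring them as not agreeing. Against the answers these people would have given it is plausible, not assured, as the 53/56 case shows.
- **The study is descriptive.** No comparative analysis is planned, so a second pass criterion would go beyond its design. This stands, and none is proposed.

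**Conclusion.** The point holds in a limited form. SAP 7.2 and SAP 7.1 together ensure that a participant who is handed the pen, does not finish and gives no answer never counts against the agreement rate for Q9 or Q11. That sits badly with a primary analysis described as being on the ENR. No planned analysis shows the result with such people scored as not agreeing.

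On that comparison, and if 48 of 51 answerers agree, one such person is worth about 2 points on both the rate and the lower limit, and two are worth 4.5 points on the lower limit. The figures at k = 5 are a ceiling. The true number may be zero, in which case nothing changes for this group. Because the threshold for the claims is redacted, one cannot say that any claim would fail. This is a cheap improvement to the plan and does not show that its headline result will be wrong.

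**What to change.** 1. In SAP 7.1, 7.2 and 14.1.2, prespecify for Q9 and Q11 a sensitivity proportion with its Clopper-Pearson interval. The denominator is every participant handed a pen; an unanswered item counts as not agreeing. Show it beside the observed-case figure. The full ENR would be a poor denominator because it includes people found ineligible before handling a pen.
2. State that the exclusions in SAP 7.2 and protocol 10.5 do not apply to this row. Otherwise the row contradicts them.
3. Reconcile those two exclusions with each other and with the statements that all consented participants, or the ENR, are analysed.
4. In SAP 9, add a discontinuation reason for not completing the pen task, separate from "Noncompliance with Protocol".

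The intended claims need not be made to depend on both figures.

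**Cost.** Some SAP wording, the matching reconciliation with protocol 10.5, one extra row for two items and one reason code. The new figure may be less favourable. It is deliberately conservative, because some blanks will have nothing to do with the pen, and the table should say so. If everyone handed a pen finishes and answers both items, the two rows agree.
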